The manufacturer of the Phoenix Thera-lase elected to seek and was awarded FDA approval under "Sec. 890.5500 Infrared lamp." The election of this classification selection was based primarily on the type of photonic energy provided which is in fact infrared light and the purpose of the superficial topical application. The product codes available for this section include a wide variety of applications, including "Lamp, Infrared, Therapeutic Heating," and "Powered Laser Non-Thermal Instruments With Non-Heating Effects For Adjunctive Use In Pain Therapy." The lower powered infrared therapeutic laser is significantly different than other medical lasers which utilize much higher power and have a purpose of altering tissue anatomy through high thermal or mechanical energy conversion. Lower power therapeutic laser therapy, as with the device used in this study, works through a conversion of the photonic energy of specific wavelengths and power to provide photochemical (biochemical) changes within the diversity of tissues that absorb the light. As such, the clinical benefits of therapeutic laser therapy in the infrared range is widely used for tissue repair, pain reduction, and resolution of inflammation, and is not attributed to the excessive production of thermal energy. The perception of a warming effect is very superficial and associated with water in the superficial layers absorbing energy. This is similar to the feeling that occurs with other infrared devices.

3. Concise Summary of Project:

Fifty consenting participants with long-standing fibromyalgia (> 3 mo duration) will be randomized to one of two treatment groups (n=25 per group) according to a computer generated randomization table. Group 1 will be the 'sham' control group and Group 2 will be the 'active' laser treatment group.

The study will be conducted in a double-blind fashion using a standard 42 watt Class IV laser which has a switch at the back of the device which allows the laser to operate in the 'inactive' mode despite giving the operator and patients the appearance of being active (e.g., generates skin warmth and a red beam of light). Treatment will be administered three times/week for three weeks. Data will be collected across the 3-week intervention and at one week and one month after completion of the intervention. Data will be analyzed with appropriate statistical methods.

4. Study Procedures:

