Potential participants will be identified through physician referral to the McDermott Center for Pain Management, as well as through advertisement via the UT Southwestern Campus Updates email blast. If participants meet screening criteria and are willing to participate, appropriate consent and HIPPA permissions will be obtained.

After consent, the participant will complete baseline outcome assessments and will be randomized to one of the two treatment cohorts, the experimental low level laser therapy group (LLLT), or the sham laser therapy group (Sham). The study investigator performing outcome assessments will be blinded to the treatment allocation group. The treating clinician will be aware of the treatment allocation assignment for laser application; however, the participant will remain blinded to the treatment cohort. Each treatment cohort will be completed as assigned—no crossover will be allowed. Each participant will receive a series of nine active laser or sham treatments on a M-W-F schedule over the three week treatment period.

The treatments will include multiple 60 sec applications over the bilateral sympathetic ganglion in the paraspinous region from T1-S2. To address the question of depth and localization of treatment, we propose that multiple tissues are being stimulated simultaneously with the application of the infrared light, including muscle, tendon, ligament, joint, and nerve. The reference to the treatment being applied over the sympathetic ganglion was not intended to suggest a primary focus of treating this structure, but rather, to standardize an anatomical landmark for where we could apply the laser treatment with the potential to stimulate the greatest number of tissues (paraspinal muscle and tendon, spinal zygapophyseal and costotransverse ligaments and joints, and sympathetic and peripheral nerves) within this region based on the superficial depth of penetration of infrared lasers of this power. Additionally, evidence supports the ability of infrared light to stimulate and positively affect the sympathetic ganglion in the lumbar spine, where the nerves are only 1 cm below the skin surface (Muneshige et al., Journal of Rehabilitation Research & Development, 2006).

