Additionally, participants will receive treatment over any tender spots reported in the hips, knees, shoulder, or elbows. Total treatment time to the spine will range from 12-14 minutes, depending on the size of the subject. Total treatment time to extremity joints will not exceed two minutes per site, so that the total treatment time to the spine and extremities will not exceed 30 minutes. All treatment for the LLLT group will be delivered at an intensity of 42 watts. The treatment will be applied via a non-contact method, with the laser applicator held 15 inches above the participant's skin. Sham treatment will be delivered via the same protocol in terms of time, application, and areas of treatment as stated above, except the laser unit will not discharge any photonic energy. Intervention will take place in the therapy room at the Health Professions Physical Therapy Clinic, which is appropriately equipped for laser administration. Application of therapeutic laser will be completed by licensed physical therapists who have completed safety training for therapeutic laser application including appropriate use of safety eyewear, room access, laser signage for laser use, and patient monitoring.

The following outcome measures will be collected at baseline: (1)Standardized SF-36 questionnaire; (2) Symptom Impact Questionnaire; (3) Current analgesic medication usage; (4) Pressure-pain threshold testing over tender points; and (5) Spinal ROM with an inclinometer and accelerometer. Outcome measures (2) and (3) will be re-assessed during the treatment phase at the end of weeks 1, 2 and 3. At 1 week and 1 month after the last laser/sham treatment session, all baseline assessments will be repeated, in addition to a global rating of change scale (-7= very harmful, 0=

neutral, +7 = very helpful). Any patient who reports any harm from the laser/sham treatments on the helpfulness scale will be queried for specific harm details. Participants randomized to Sham will have the option of receiving LLLT treatments after they complete their study enrollment.

5. Sub-Study Procedures:

Not applicable for this study.

6. Criteria for Inclusion of Subjects:

- 1) 18-80 years old
- 2) Pre-existing medical conditions are under stable control
- 3) Diagnosis of fibromyalgia by standard criteria (e.g., pain in all four body quadrants for over 3 months, 11 of 18 tender points, bilaterally in the cervical and upper thoracic back areas, and chronic fatigue)

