Evaluation of the a-priori sample size was calculated utilizing a power analysis. This analysis was based on the primary outcome measure (pain) being a continuous response variable. Data from previous published research on the projects primary intervention conducted over longer periods of treatment time supports an effect size of 0.4 on the impact of Class III light therapy techniques. Power calculations for the current project were based on mean differences between two dependent groups (matched pairs), power (1- β probability) = 0.80, α error probability = 0.05, and effect size of 0.4 (GPower ver. 3.1). These parameters resulted in a total sample size calculation of 52 to reject the null hypothesis. Accounting for a dropout rate of no more than 15%, a final sample size of 60 was selected. Dependent variables will be evaluated with non-parametric analysis for reports of patient well-being, while repeated measure ANOVAs will be utilized for changes of significance over time in pain, quality of life, function, ROM, and pressure-pain threshold. Significance will be set at p<0.05.

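### Section 14 sizes the trial with a matched-pairs calculation, but sham and active are independent randomised groups, so the stated 80% power for that comparison is unsupported

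*Combined protocol and SAP*

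**What the plan says.** Section 14 (Biostatistics) gives the basis of the sample size: "Power calculations for the current project were based on mean differences between two dependent groups (matched pairs", with "power (1- β probability) = 0.80", alpha 0.05 and an effect size of 0.4. The result is "These parameters resulted in a total sample size calculation of 52 to reject the null hypothesis", which is then raised to 60 for dropout of up to 15%. The 0.4 comes from earlier published work that "supports an effect size of 0.4 on the impact of Class III light therapy techniques". Section 14 does not say whether that is a within-patient or a between-group effect.

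The design is in Sections 3 and 4. Participants "will be randomized to one of two treatment groups (n=25 per group) according to a computer generated randomization table", one group sham and the other active. Each stays in the assigned cohort, and "no crossover will be allowed". No matching of sham to active participants is described.

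For the analysis, Section 14 says that "repeated measure ANOVAs will be utilized for changes of significance over time in pain, quality of life, function, ROM, and pressure-pain threshold". It names no between-arm contrast, visit, covariate or correlation.

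**The concern.** A matched-pairs calculation is valid when each observation in one condition has a partner in the other, through crossover or matching. This trial has neither between its arms. The only paired data are each participant's own repeated measurements. A test on 52 such pairs would combine sham and active participants and ask whether pain changed over time, which says nothing about laser against sham.

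Two things are at stake. The number enrolled has no valid justification for the comparison that randomisation exists to support, so a null result could be read as evidence of no effect when the trial may have had little chance of finding one. And because both the sizing and the analysis sentence are framed around change over time, a significant overall change could be mistaken for efficacy.

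**Working it through.** All figures are two-sided at 0.05. Power comes from the noncentral t or F distribution. n is the number per arm, or the number of pairs in step 1.

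**Inputs from the documents.** Section 14: effect size 0.4, power 0.80, alpha 0.05, total 52, dropout 15%, final total 60. Section 3: 25 per group. Section 4: five post-baseline assessments (weeks 1, 2 and 3, then 1 week and 1 month after treatment) for the Symptom Impact Questionnaire and analgesic use; two (1 week and 1 month) for the other baseline measures.

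**Assumptions.** The documents give no correlations, so 0.5, 0.7 and 0.8 are used, equal between all visits. Unless stated otherwise, 0.4 is a between-group difference in SD units, constant after baseline.

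**1. The plan's own figure.** Paired t-test, noncentrality 0.4 × √n, df n − 1.
- n = 51: power 0.7999. n = 52: 0.4 × √52 = 2.88, power 0.8078. So 52 is reproduced exactly. A one-sided test would need 41.
- The same test within a single arm has power 0.484 at n = 25, 0.500 at n = 26 and 0.563 at n = 30.

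**2. Sham versus active, unadjusted, one visit.** Noncentrality 0.4 × √(n/2), df 2n − 2.

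| n per arm | Power |
|---|---|
| 21 (25 × 0.85 = 21.25) | 24% |
| 25 | 28% (0.4 × √12.5 = 1.41) |
| 26 | 29% |
| 30 | 33% |
| 100 | 80% |

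The difference detectable with 80% power is 0.81 SD at 25 per arm and 0.74 SD at 30 per arm.

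**3. Baseline-adjusted mean of k follow-up visits.** Variance multiplier v = (1 + (k − 1)r)/k − r², noncentrality 0.4 × √(n/(2v)), df 2n − 3. For example, k = 1 and r = 0.5 give v = 0.75.

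| Follow-ups averaged | n per arm | r = 0.5 | r = 0.7 | r = 0.8 |
|---|---|---|---|---|
| 1 | 25 | 36% | 49% | 64% |
| 1 | 30 | 42% | 57% | 72% |
| 2 | 25 | 50% | 64% | 78% |
| 5 | 25 | 65% | 76% | 87% |
| 5 | 30 | 73% | 83% | 93% |

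With one follow-up and r = 0.5, 80% power needs 0.70 SD at 25 per arm or 0.64 SD at 30 per arm.

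**4. Group-by-time test in a six-visit repeated measures ANOVA.** This is the natural between-arm reading of the analysis that Section 14 names. λ = 2n × Σ(c/2)²/(1 − r), with c the between-arm difference at each visit minus its mean over visits; df 5 and 5(2n − 2). The differences are 0 at baseline and 0.4 at five visits, mean 0.333, so Σc² = 0.333² + 5 × 0.067² = 0.133. At n = 25 and r = 0.5, λ = 50 × (0.133/4)/0.5 = 3.33.

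| n per arm | r = 0.5 | r = 0.7 | r = 0.8 |
|---|---|---|---|
| 25 | 24% | 39% | 57% |
| 30 | 29% | 47% | 67% |

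**5. Simulation check at 25 per arm (20,000 runs, r = 0.5 / 0.7 / 0.8).** Group-by-time: 0.241 / 0.394 / 0.577. Adjusted mean of five: 0.635 / 0.746 / 0.867. The formula in step 3 therefore runs about a percentage point high at r = 0.5 and 0.7, because it ignores chance baseline imbalance.

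**6. If 0.4 were Cohen's f.** For two groups d = 2f = 0.8, and unadjusted power is 72% at 21 per arm, 79% at 25, 81% at 26 and 86% at 30.

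**The case against.** Nobody can say from the documents that the trial is underpowered. A paired effect size cannot be turned into a between-group one without a correlation, and none is given. Treating 0.4 as a between-group difference is therefore a choice, and the resulting range is very wide. Repeated measures can also recover much of the power: the adjusted mean of five follow-ups exceeds 80% at 25 per arm when the correlation is 0.8. The group-by-time test gets there too if the correlation is high enough (at 25 per arm, 72% at 0.85 and 90% at 0.9; at 30 per arm, 81% and 95%). Finally, the f reading in step 6 also gives a balanced total of exactly 52, and Section 14 does plan ANOVAs, so matched pairs might be a mislabel on a sound calculation.

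The first point stands, and it limits the conclusion: the 80% is unsupported, not shown to be false by a known amount. The second does not rescue the plan, because it specifies no averaged contrast, covariate or correlation. Five follow-ups also exist only for some measures: "Outcome measures (2) and (3) will be re-assessed during the treatment phase at the end of weeks 1, 2 and 3". The third is possible but contradicts the words used, since Section 14 names matched pairs and never mentions f. Even on that reading, 25 per arm gives 79%, and 72% after 15% dropout. That two effects differing so much can yield the same 52 is a reason to define 0.4.

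**Conclusion.** The concern holds. The arithmetic in Section 14 is right for the test it names, but that test is not the randomised comparison, and nothing else in the documents supplies power for sham versus active. This conclusion needs no assumption beyond the stated design.

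The size of any shortfall does rest on assumptions. With 0.4 as a between-group standardised difference, power at 25 per arm is 28% unadjusted at one visit. Over correlations of 0.5 to 0.8, it runs from 24% (group-by-time, 0.5) to 87% (adjusted mean of five visits, 0.8). In that range the six-visit group-by-time test stays below 80% at both 25 and 30 per arm; higher correlations could change this. This must be fixed, because the plan states a power that its calculation does not deliver for its main comparison.

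**What to change.** Replace the matched-pairs calculation with an independent-groups calculation for the between-arm contrast that will be tested. Name the pain measure, the visit or average of visits, and any baseline covariate. State what 0.4 means and any assumed correlation. Delete the claim of 80% power at 0.4 unless the new calculation supports it, and restate the power or detectable effect for the number enrolled. Section 3 plans 50 and Section 14 selects 60, so that must be settled at the same time. Report the between-arm difference with its 95% confidence interval.

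Possible wording, if a single-visit adjusted comparison is chosen: *With 25 (30) per arm, two-sided alpha 0.05 and an assumed baseline correlation of 0.5, the baseline-adjusted comparison at one visit has 36% (42%) power for a standardised difference of 0.4 and 80% power for 0.70 (0.64).*

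The cost is a rewrite of Section 14 and a commitment to one between-arm contrast. No extra patients are required if the team accepts the restated power, which is likely to be less favourable. For comparison, holding 80% power at 0.4 SD with an unadjusted single-visit test would take about 100 completers per arm.

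### Section 14 sizes a two-arm sham-controlled trial as matched pairs, and names neither a laser-versus-sham test nor a primary pain score

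*Combined protocol and SAP*

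**What the plan says.** **Design.** Section 3 says that participants "will be randomized to one of two treatment groups (n=25 per group"), and that "Group 1 will be the 'sham' control group". Section 4 adds that "no crossover will be allowed". No section describes matching of participants.

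**Sizing (Section 14).** "Power calculations for the current project were based on mean differences between two dependent groups (matched pairs"), with power 0.80, alpha 0.05 and effect size 0.4. "These parameters resulted in a total sample size calculation of 52 to reject the null hypothesis". An allowance for dropout takes this to 60. Section 3 has 50. The two totals need reconciling; both are used below.

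**Outcome and test (Section 14).** "This analysis was based on the primary outcome measure (pain) being a continuous response variable". The test is given as "repeated measure ANOVAs will be utilized for changes of significance over time in pain, quality of life, function, ROM, and pressure-pain threshold". Patient well-being goes to an unspecified non-parametric analysis. Section 3 otherwise promises only suitable methods.

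**Assessments (Section 4).** All measures are taken at baseline and at one week and one month after the last session. In addition, "Outcome measures (2) and (3) will be re-assessed during the treatment phase at the end of weeks 1, 2 and 3"; measure (2) is the Symptom Impact Questionnaire and (3) is analgesic use. The questionnaire is therefore assessed six times and the SF-36 three times. Neither is tied to the word pain, and no visit is called primary.

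**The concern.** A sham arm exists so that placebo response, natural fluctuation and regression to the mean can be subtracted. That needs a comparison between arms. Section 14 describes a within-person question twice: in the wording of the test, and in the model used for sample size. Nothing elsewhere supplies the between-arm contrast.

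Two things are at stake. The stated 80% power belongs to a comparison that the design does not make, so the plan gives no power for laser versus sham. And if the test were run as worded, a significant time effect could be reported that says nothing about the laser. With no score designated, the choice of pain measure also stays open until the data are seen.

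**Working it through.** **1. Reproducing 52.** Inputs from Section 14: effect 0.4, alpha 0.05, power 0.80, matched pairs. Sidedness is not stated. For a paired t-test the noncentrality is 0.4 × √n on n − 1 degrees of freedom.
- n = 51: 0.4 × √51 = 2.857, two-sided power 0.7999.
- n = 52: 0.4 × √52 = 2.884, two-sided power 0.808.

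So 52 is the smallest n that reaches 0.80. A one-sided test would give 41. The arithmetic is correct for a two-sided paired test, and 52 × 1.15 = 59.8 accounts for the 60.

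**2. What a literal time test would detect.** Assumptions not in the documents: no laser effect, the same shift s (in SD) in both arms at every post-baseline visit, equal correlation r between visits, N = 50, and k = 3 or 6 assessments. The F test for time has k − 1 and (N − 2)(k − 1) degrees of freedom and noncentrality N × s² × (k − 1) / [k × (1 − r)]. For s = 0.2, k = 3, r = 0.5 this is 50 × 0.04 × (2/3) / 0.5 = 2.667 on 2 and 96 degrees of freedom, so the test is significant in 28.2% of trials.

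| Shared shift | r = 0.3 (k = 3 / 6) | r = 0.5 (k = 3 / 6) | r = 0.7 (k = 3 / 6) |
|---|---|---|---|
| 0.2 SD | 21.1% / 17.8% | 28.2% / 24.0% | 44.3% / 39.3% |
| 0.4 SD | 68.0% / 64.1% | 82.9% / 80.7% | 96.9% / 96.7% |

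Under the same null, the simulated group-by-time test rejected in 5.0-5.4% of trials (8,000 runs).

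**3. Power for laser versus sham if 0.4 is a between-arm difference in SD units.** This is an assumption. So are equal arms, no dropout and, for rows with adjustment, equal correlation r of 0.3 to 0.7. With n per arm the noncentrality is (0.4 / √V) × √(n/2). V is 1 unadjusted. For the baseline-adjusted mean of m post-baseline visits, V = [1 + (m − 1)r]/m − r², and one further degree of freedom is lost.
- m = 1: V = 1 − r² = 0.91, 0.75, 0.51 for r = 0.3, 0.5, 0.7.
- m = 2 (three assessments): V = 0.56, 0.50, 0.36.
- m = 5 (six assessments): V = 0.35, 0.35, 0.27. For r = 0.5, (1 + 2)/5 − 0.25 = 0.35.

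| Test | 25 per arm | 30 per arm | n per arm for 80% |
|---|---|---|---|
| Unadjusted, one visit | 28% | 33% | 100 |
| Adjusted, one visit | 31-49% | 36-57% | 52-91 |
| Adjusted mean of two visits, constant effect | 46-64% | 53-72% | 37-56 |
| Adjusted mean of five visits, constant effect | 65-76% | 73-83% | 28-36 |

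**4. Sensitivity of the averaged contrast.** Simulations of a mixed model at r = 0.5 with 15% dropout (1,200 runs per cell) gave, at 25 and 30 per arm with six assessments, 60% and 70% for a constant effect, 35% and 41% for one that builds up and then halves at one month, and 39% and 44% for one that fades. With three assessments they gave 47% and 52% for a constant effect, and 26% and 31% if it halves at one month.

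**5. Detectable difference.** For 80% power, unadjusted, it is 0.81 SD at 25 per arm and 0.74 SD at 30 per arm.

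**The case against.** The strongest reply is that the between-arm comparison is obvious. The title says sham-controlled, Group 1 is labelled the control and outcome assessors are blinded to allocation. A repeated-measures ANOVA in a two-arm trial ordinarily carries group and group-by-time terms, and group-by-time is a valid test. This has weight. A reader might infer from step 2 that the sponsor plans to claim efficacy from a pooled time effect. The documents do not support that: the term is unstated, which is not the same as a declared intention. The rates in step 2 apply only to the literal reading. The reply does not rescue the sizing, which names matched pairs outright and reproduces on that basis.

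It may also be said that 52 fits a group-by-time test. It does, for Cohen's f = 0.2 with two time points and correlation 0.5. Section 14 states none of these, and Section 4 has three or six assessments. Moreover, f = 0.2 there means cell deviations of ±0.2 SD, so changes of +0.4 and −0.4 in the two arms: a between-arm difference in change of 0.8 SD, not 0.4.

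A reader might also infer that the trial has only 28-33% power and has to be enlarged. That does not follow. Section 14 does not say whether 0.4 is within-person or between-arm, and an adjusted average reaches 83% in one case at 30 per arm.

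Finally, the absence of a primary visit is a weaker gap than the rest. An omnibus group-by-time test over fixed visits needs none.

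**Conclusion.** The point holds. The sample-size model is wrong for the design as written: 52 is correct arithmetic for a paired comparison, and the 80% attached to it is not power for laser versus sham. This rests only on Sections 3, 4 and 14. The missing between-arm contrast and the missing primary pain score are gaps in specification. Because Section 14 lists pain separately from pressure-pain threshold, a self-report score is the natural reading, but none is designated.

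The size of the power shortfall is conditional. It depends on reading 0.4 as a between-arm effect, on assumed correlations, on the shape of the effect over time and on dropout; the range runs from about a quarter to just above 80%. The sponsor should correct this before the data are seen. The design itself can answer the question once the analysis is written down.

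**What to change.** In Section 14:
1. State that efficacy is judged by a between-arm test at two-sided 0.05: either the group-by-time interaction, or a prespecified baseline-adjusted active-minus-sham contrast at one visit or averaged over post-baseline visits. State that time effects and within-arm changes are not evidence of efficacy.
2. Designate one self-report score already collected as the primary pain measure. Name a primary visit or average only if a single contrast is chosen, with the reason for expecting the effect then.
3. Restate power for two independent arms and the chosen test, and say whether 0.4 is a within-person or a between-arm effect.

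**Cost.** A few sentences and a new power statement; no new data or visits. The restated power will probably be below 80% for most choices. The sponsor may then report the detectable effect or call the trial exploratory; this point does not require a larger trial.

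The choice of test is a trade-off. In simulations with 21 completers per arm, an effect of 0.8 SD, correlation 0.5 and six assessments, a one-week contrast had 30% power against 79% for group-by-time when the effect faded. An average had 40% against 91% when the effect appeared only after treatment. Under a constant effect the average does well (step 3). The choice should follow the expected time course.

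### Section 14 plans repeated-measures ANOVA with no analysis set or missing-data method; in its classical form it would drop about 9 of 60 randomised participants at the plan's own dropout rate

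*Combined protocol and SAP*

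**What the plan says.** Section 14 describes the primary outcome as follows: "This analysis was based on the primary outcome measure (pain) being a continuous response variable". It names neither the pain instrument nor the primary visit. For pain and the other continuous outcomes, "repeated measure ANOVAs will be utilized for changes of significance over time in pain, quality of life, function, ROM, and pressure-pain threshold". On attrition it says only "Accounting for a dropout rate of no more than 15%, a final sample size of 60 was selected".

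Section 4 (Study Procedures) sets two measurement schedules. The Symptom Impact Questionnaire and analgesic use are taken weekly during treatment: "Outcome measures (2) and (3) will be re-assessed during the treatment phase at the end of weeks 1, 2 and 3". Everything else waits until after treatment: "At 1 week and 1 month after the last laser/sham treatment session, all baseline assessments will be repeated".

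Nowhere does the document define an analysis set, a missing-data method, a mixed model, imputation or a sensitivity analysis. The nearest text is the ban on crossover in Section 4. That governs which treatment is delivered, not who is analysed.

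**The concern.** Repeated-measures ANOVA in its classical form needs a full row of visits for each participant and discards anyone with a gap. A participant who stops after week 1, or misses one weekly form, would then contribute nothing, although scores had been recorded. The comparison becomes one among completers rather than one among the participants as randomised.

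Two things are at stake. If the reasons for leaving differ by arm and relate to how participants are doing, the completers' difference can be biased. Even without bias, data already collected are set aside. Enrolling more participants restores numbers but does not address either problem.

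**Working it through.** **1. The plan's own figures.** Inputs from Section 14: matched-pairs test, effect size 0.4, "power (1- β probability) = 0.80", "α error probability = 0.05". The exact two-sided paired t calculation gives N = 52 (power 0.808). For dropout, 52 × 1.15 = 59.8, rounded up to 60. Both stated figures reproduce. (Dividing by 0.85 would give 61.2, so 62; this does not affect the point.)

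**2. Participants lost under complete-series analysis.** At 15%, 60 × 0.15 = 9 are dropped and 51 kept. At 10%, 6 are dropped; at 5%, 3. Section 3 gives a total of 50 instead of 60; on that figure, 50 × 0.15 = 7.5, so 7 or 8 are dropped.

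**3. What data those participants would have (Section 4).**

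| Outcome | Time points | Held by someone who leaves during treatment |
|---|---|---|
| Symptom Impact Questionnaire | 6: baseline, weeks 1, 2, 3, then 1 week and 1 month after | Baseline and any weekly scores reached |
| SF-36, range of motion, pressure-pain threshold | 3: baseline, 1 week and 1 month after | Baseline only |
| Pain (primary) | Instrument not named | Weekly scores only if taken from the questionnaire |

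If all 9 leave after at least one weekly score, at least 9 × 2 = 18 observed questionnaire scores are discarded.

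**4. Sporadic gaps (assumed rates; the document gives none).** With 5% missing independently at each of five post-baseline visits, 1 - 0.95^5 = 0.226 of participants are deleted, leaving 60 × 0.95^5 = 46.4. At 3% the loss is 1 - 0.97^5 = 0.141. For the three-visit outcomes, 5% per visit deletes 1 - 0.95^2 = 0.0975.

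**5. Bias, by simulation.** Assumptions: six visits, SD 1, equal within-person correlation of 0.5 or 0.7, 15% leaving each arm after week 1, and 400,000 participants per arm so that sampling error is negligible. In sham, departure depends on poor week-1 change (log-odds 1.5 per SD); in active it is random. Positive values favour laser. The contrast in the first two rows is change from baseline to the last visit.

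| Analysis | True 0.40 | True 0 |
|---|---|---|
| Completers, change from baseline | 0.31 to 0.34 | -0.06 to -0.09 |
| Likelihood-type, using baseline and week 1 | about 0.40 | about 0 |
| Completers, raw last-visit difference | about 0.40 | about 0 |
| Completers, baseline-adjusted | about 0.36 | -0.04 to -0.05 |

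With the same dropout rule in both arms, the completers' bias is about 0.

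A harsher case used 30 per arm, with poor scorers leaving sham and good scorers leaving active, and compared last-visit means. A true 0.40 became 0.28, 0.23 and 0.16 at correlations 0.4, 0.6 and 0.8, while the all-visits likelihood model gave 0.40 to 0.41. Reversing who leaves would reverse the direction.

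**6. Precision.** With dropout unrelated to scores and 30 per arm, the standard error is about 0.28 for completers and 0.26 to 0.28 for the likelihood model.

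**The case against.** The strongest reply is that the plan never says incomplete participants are deleted. It names a family of methods and is silent on gaps, on which visits enter each model, and on software. That is correct: deletion is inferred from the method's name together with the silence. But nothing in the document replaces it, and if a mixed model was intended, Section 14 has to say so, which is the same amendment.

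Second, nothing in the document shows when or why participants will leave. Sham participants are offered laser treatment after finishing the study, which is a reason to stay, and participants are meant to be blinded. This stands, and the dropout scenarios above are assumptions.

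Third, the modelled bias is modest. Against a standard error of about 0.28, a null bias of 0.06 to 0.09 is 0.2 to 0.3 standard errors. It depends on analysing change from baseline, since the raw last-visit difference is unbiased in the same scenario. This also stands.

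A reader might go further and infer that the planned analysis will make laser look better than it is. The document does not support that. It gives no pattern of withdrawal, and in the sham-only scenario the error runs against laser. Nor can one infer that most withdrawals will have usable scores on every outcome: three of the measures have no on-treatment assessments.

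**Conclusion.** The concern holds in limited form. Dropout is foreseen and treated only as lost sample size, and the named method, read in its usual sense, removes about 9 of 60 randomised participants from the comparison. That count rests on the plan's 15% and on the classical form of the ANOVA.

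The recoverable information is mainly in the Symptom Impact Questionnaire. It extends to the primary outcome only if pain is taken from that instrument. Bias ranges from none to material, in either direction, depending on who leaves. Lost precision alone would be a weak reason for change. The reason to act is that the plan has no rule keeping randomised participants with observed data in their arm, and a better method is available at little cost.

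**What to change.** In Section 14, replace repeated-measures ANOVA with a likelihood-based mixed model for repeated measures that includes all randomised participants in their assigned arm with all observed scores.

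- **Terms:** arm, visit, arm-by-visit and baseline score. With baseline as a covariate, a participant with no later score drops out. Modelling baseline as a response with a mean common to both arms keeps such participants in, though they add little on the treatment difference.
- **Covariance:** unstructured, with Kenward-Roger degrees of freedom and a pre-specified simpler structure if the model does not converge. The fallback matters at this size: five post-baseline visits need 5 × 6 / 2 = 15 covariance parameters, and six visits need 6 × 7 / 2 = 21.
- **Reporting:** number and timing of withdrawals by arm.
- **Sensitivity:** one analysis for data missing not at random, since the main model assumes missing at random.
- **Clarification:** state which instrument supplies pain, so that the visits entering the primary model are known.

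The cost is SAP wording and slightly more analysis work, with no added visits or participants. The downside is reliance on missing at random, which is a weaker assumption than the complete-series ANOVA needs.
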